6.1.6 Regulatory Release to Site

Not applicable. Off-shelf IMP use from the hospital pharmacies.

6.1.7 Destruction of Trial Drug

Unused drug will be returned to community pharmacies by participants or to participating hospital pharmacies if more convenient for destruction as per usual practices at participating pharmacies. There are no special requirements for LACI-3.

6.1.8 Summary of Product Characteristics (SPC) Booklet or Investigators Brochure

The Representative Summary of Product Characteristics (SPC) (for cilostazol, isosorbide mononitrate slow release, and isosorbide mononitrate, generic) is provided in a separate document with a cover sheet and signature page (signed and verified by the CI and Co-Sponsors) and is filed in the TMF.

6.2 PLACEBO

There is no placebo.

The comparator will be a standard care alone including guideline stroke secondary prevention prescribed post-stroke as per national guidelines.

6.2.1 Labelling and Packaging

Not applicable. Off-shelf IMP use from the hospital pharmacies.

6.2.2 Storage

Not applicable.

6.3 DOSING REGIME

Patients will be supplied with trial drug in its usual (marketing) packaging unaltered. Patients will be issued with instructions reflecting the allocated dosing schedule which will instruct them what tablets they have to take initially and how to increase the dose. They will receive a phone call after 1 to 2 and 3 to 4 weeks as per schedule below to guide dose escalation. If a patient encounters intolerable side effects they will be asked to return to the highest previously tolerated dose and this will be recorded in the eCRF and hospital notes. They will be given clear instructions by phone or in person (depending on the stage of the trial).

Patients will also receive instruction on how they should decrease the dose of trial drug incrementally at the end of the study.

Table 1: Patients randomised to Isosorbide Mononitrate alone - either XL or non-XL preparations, example. If a slow release preparation is not available, then a non-slow release preparation may be used, but the dose should be given half in the morning (e.g. 08.00 am) and half in the evening (e.g. 18.00hrs)

ISMN XL Dosing Regime		ISMN non-XL Dosing Regime			
David	ISMN XL 25mg		Davi	ISMN non-XL 20mg	
Day	Morning	Evening	Day	Morning	Evening
1-5	25mg	nil	1-5	nil	20mg
6-10	50mg	nil	6-10	20mg	20mg
11-15	50mg	nil	11-15	20mg	20mg
16-20	50mg	nil	16-20	20mg	20mg
At end of study		At end of	fstudy		
Week	Morning	Evening	Week	Morning	Evening
79	25mg	Nil	79	20mg	Nil
80	Nil	Nil	80	Nil	Nil

Table 2: Patients randomised to cilostazol alone

Cilostazol Dosing Regime					
Devi	Cilostazol				
Day	Morning	Evening			
1-5	Nil	50mg			
6-10	50mg	50mg			
11-15	50mg	100mg			
16-20	100mg 100mg				
At end of s	At end of study				
Week	Morning Evening				
79	50mg	50mg			
80	Nil	Nil			

Table 3: Patients randomised to both Isosorbide Mononitrate and Cilostazol

ISMN XL/Cilostazol Dosing Regime						
-	Isosorbide Mononitrate XL 25mg		Cilostazol			
Day	Morning	Evening	Morning	Evening		
1-5	25mg	nil	Nil	Nil		
6-10	50mg	nil	Nil	Nil		
11-15	50mg	nil	Nil	50mg		
16- 20	50mg	nil	50mg	50mg		
21-25	50mg	nil	50mg	100mg		
26-30	50mg	nil	100mg	100mg		
At end of stu	At end of study					
Week	Morning	Evening	Morning	Evening		
79	25mg	Nil	50mg	50mg		
80	Nil	Nil	Nil	Nil		

ISMN non-XL/Cilostazol Dosing Regime					
Davi	Isosorbide Mononitrate 20mg		Cilostazol		
Day	Morning	Evening	Morning	Evening	
1-5	nil	20mg	Nil	Nil	
6-10	20mg	20mg	Nil	Nil	
11-15	20mg	20mg	Nil	50mg	
16- 20	20mg	20mg	50mg	50mg	
21-25	20mg	20mg	50mg	100mg	
26-30	20mg	20mg	100mg	100mg	
At end of study					
Week	Morning	Evening	Morning	Evening	
79	20mg	Nil	50mg	50mg	
80	Nil	Nil	Nil	Nil	

Table 4: Patients randomised to neither Isosorbide Mononitrate or Cilostazol

Neither ISMN/Cilostazol Dosing Regime						
_	Isosorbide Mononitrate		Cilostazol			
Day	Morning	Evening	Morning	Evening		
1-4	Nil	Nil	Nil	Nil		
5-8	Nil	Nil	Nil	Nil		
9-12	Nil	Nil	Nil	Nil		
13, 14	Nil	Nil	Nil	Nil		
At end of s	At end of study					
Week	Morning	Evening	Morning	Evening		
79	Nil	Nil	Nil	Nil		
80	Nil	Nil	Nil	Nil		

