3. STUDY DESIGN

LACI-3 will be an investigator-led, Phase III, prospective, randomised, controlled, 2x2 partial factorial, open label, blinded outcome trial performed in multiple UK hospital-based centres. LACI-3 is open to support international collaboration. The trial received Scientific Advice from the Medicines and Health Care Regulatory Agency assisted by NHS England Medicines Repurposing Programme at a meeting on 2nd July 2024. All MHRA guidance has been incorporated into the design of LACI-3.

Duration: The trial will last for 52 months with the treatment phase for each participant starting from within one day of randomisation until the end of trial follow-up at 18 months.

Participants meeting inclusion/exclusion criteria will be randomised at participating hospitals.

Participants will be randomised to start one of four treatments; ISMN only; cilostazol only; both ISMN and cilostazol; or neither ISMN nor cilostazol. Patients with contraindications to cilostazol can be randomised to ISMN versus no ISMN arms only; patients with contraindications to ISMN can be randomised to cilostazol versus no cilostazol arms only. The partial factorial design allows testing of both drugs when given alone and together. As in LACI-2, the doses will be escalated until participants are on their full dose by 1 month. If a patient encounters intolerable side effects at full dose, then they will be able to remain on the highest dose regime that they can tolerate and this dose will be recorded. The total duration of the trial drug administration will be 18 months. After the end of follow-up, the patients will reduce the tablets over about two weeks and then stop the trial medication. They will return any unused drug to their local community pharmacy or the hospital pharmacy if more convenient for destruction.

Drug supply: Trial drug will be dispensed by hospital pharmacies. The first drug supply will be given at the randomisation visit if allocated to the IMP. The IMP re-supply for the followup at 6 and 12 months will be posted to participants. Participants can collect the IMP resupply in person from the recruiting site.

Participants should continue their allocated treatment until the end of 18-month follow-up.

Discontinuing the allocated treatment by the participant's direct clinical care team due to the occurrence of an outcome event does not constitute withdrawal.

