6.4 DOSE CHANGES

Doses will be initiated as per the example regime in section 6.3. Patients will be allowed to increment the dose more slowly, or to stay at a previously tolerated dose where their symptoms preclude reaching the target dose stated in 6.3. Variation of dose like this will not count as a protocol deviation. Patients will be able to stay on the dose they can tolerate. If necessary, this will be done under close guidance of the researcher. There will be no other changes to the doses described in section 6.3.

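### The end-of-study dose rows in section 6.3 presume the target dose: for participants held lower they give no reduction at three steps and an increase at one, and the taper length does not sit cleanly with section 3

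*Protocol*

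**What the plan says.** Three parts of the protocol bear on how trial drug ends.

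- **Direction and length.** Section 6.3 states: "Patients will also receive instruction on how they should decrease the dose of trial drug incrementally at the end of the study". Section 3 adds: "After the end of follow-up, the patients will reduce the tablets over about two weeks and then stop the trial medication".
- **The schedule.** Tables 1-3 of section 6.3 end with rows for weeks 79 and 80. For ISMN, with XL on the left and non-XL on the right, they read "79 25mg Nil 79 20mg Nil" and then "80 Nil Nil 80 Nil Nil". For cilostazol, alone or in combination, week 79 is 50 mg morning and evening, and week 80 is nil. No row depends on the dose the participant is taking.
- **Lower doses are allowed.** Sections 3 and 6.3 let a participant with intolerable side effects stay at, or return to, the highest dose they tolerated, and have that dose recorded (section 6.3: in the eCRF and hospital notes). Section 6.4 agrees, "Patients will be able to stay on the dose they can tolerate", and says this is not a deviation. The section closes: "There will be no other changes to the doses described in section 6.3".

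**The concern.** The end-of-study rows read as if every participant had reached the target dose. The protocol expects that some will not, and permits them to spend the trial on an earlier escalation step. Applying a fixed week-79 dose to those participants need not lower it, and at the lowest cilostazol step it would raise it.

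Those participants are, by construction, the ones who tolerated the drug least. At stake is their safety in the days around stopping, when a step described as a decrease could take them back to a dose that they had not tolerated. Sections 6.8, 7.2 and 10 keep safety reporting open until two weeks after the last dose, so any resulting events would fall within the trial's own reporting period.

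**Working it through.** **Inputs.** All come from section 6.3, Tables 1-3.

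- Cilostazol steps: 50 mg in the evening (50 mg/day); 50 mg twice daily (100 mg/day); then "11-15 50mg 100mg" (150 mg/day); then the target, 100 mg twice daily (200 mg/day).
- ISMN first step, XL then non-XL: "1-5 25mg nil 1-5 nil 20mg". Targets in the tables: XL 50 mg/day, and non-XL 20 + 20 = 40 mg/day.
- Week 79: cilostazol 50 + 50 = 100 mg/day; ISMN XL 25 mg/day; ISMN non-XL 20 mg/day, in the morning.

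**Formula.** Ratio = week-79 daily dose / daily dose held until then. A ratio below 1 is a decrease, 1 is no change, and above 1 is an increase.

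| Preparation | Dose held (mg/day) | Week 79 (mg/day) | Ratio | Effect |
|---|---|---|---|---|
| Cilostazol, target | 200 | 100 | 100/200 = 0.5 | halved |
| Cilostazol | 150 | 100 | 100/150 = 0.67 | reduced by a third |
| Cilostazol | 100 | 100 | 100/100 = 1.0 | unchanged |
| Cilostazol, first step | 50 | 100 | 100/50 = 2.0 | doubled |
| ISMN XL, target | 50 | 25 | 25/50 = 0.5 | halved |
| ISMN XL, first step | 25 | 25 | 25/25 = 1.0 | unchanged |
| ISMN non-XL, target | 40 | 20 | 20/40 = 0.5 | halved |
| ISMN non-XL, first step | 20 | 20 | 20/20 = 1.0 | same total, moved from evening to morning |

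The target rows come first as a check on intent: the schedule gives the same proportionate step, one half, from target for all three preparations. That fits a row written with the target dose in mind. Of the five below-target rows, one is a decrease, three are unchanged and one is an increase.

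**Length.** The tables show a reduced, non-zero dose in week 79 only, and nil in week 80. That is one week on a reduced dose, against about two weeks in section 3.

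**Timing.** Eighteen months is 18 x 365.25 / 12 / 7 = 78.3 weeks, so week 79 falls where 18 months of treatment end. Section 3 places the reduction after the end of follow-up.

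**The case against.** The best defence is that nobody would read the week-79 row as an order to raise a dose. The governing sentence speaks of a decrease. The Table 1 heading calls its content an example, and section 6.4 describes the 6.3 regime as an example. Section 6.4 lets participants stay on what they tolerate, and its closing sentence about other changes can fairly be read as leaving that allowance intact. Sites also have the means to tailor the last step: the tolerated dose is recorded, each prescription form records drug and dose, and section 6.9 has the site telephone about three weeks before the 18-month follow-up.

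Much of this stands as mitigation. It makes an actual increase less likely, and it means that the last sentence of 6.4 should not be pressed as a bar on tailoring. It does not close the gap. Section 6.4 uses the example label only for how doses are initiated, Tables 2 and 3 do not carry it, and permission to stay on a dose does not say how to step down from it. Nothing makes the end-of-study row depend on the current dose.

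Four stronger readings might be inferred, and the documents do not support them.

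- *Everyone below target has the dose doubled or left unchanged.* Doubling arises at one cilostazol step only and never for ISMN, and the 150 mg/day cilostazol step does receive a reduction.
- *Participants with an unchanged dose are harmed by stopping abruptly in week 80.* Target-dose participants take the same last step, from the same week-79 dose to nil. Whether a further step is needed is a clinical judgement that the protocol does not inform.
- *The numbers affected can be estimated from LACI-2.* The 75% figure in section 1.1 is a target, reported as exceeded, for taking at least half of allocated drug. It is not a distribution of dose steps.
- *The 18-month endpoint is disturbed.* Section 3 puts the reduction after follow-up.

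On length, the rows do span two calendar weeks, 79 and 80, and section 3 says only about two. The discrepancy turns on whether a week of nil counts as reduction.

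**Conclusion.** The concern holds in a limited form. Read as written, the week-79 rows are a reduction only from the target dose (ratio 0.5) and from cilostazol 150 mg/day (0.67). They are no reduction for a participant held at cilostazol 50 mg twice daily, ISMN XL 25 mg or ISMN non-XL 20 mg. For one held at the first cilostazol step they are an increase, from 50 to 100 mg/day. That contradicts section 6.3's own statement that the dose is decreased incrementally. The one-week against two-week wording is a real but softer inconsistency.

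The conclusion assumes that the rows are applied literally and that a participant is still held at one of the tabulated steps when week 79 begins. How many that would be cannot be derived from the protocol. No endpoint, sample size, power or analysis figure is affected. The matter is one of participant safety and clear instructions. It should be corrected because, at one step, the written schedule points in the wrong direction.

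**What to change.** Reconcile the end-of-study rows of Tables 1-3 in section 6.3, and the patient instructions drawn from them, with the tolerated-dose allowance in sections 3, 6.3 and 6.4. The text should make clear how the end-of-study instruction relates to the dose a participant is actually taking, using the dose already recorded in the eCRF. Make the length of the reduction in section 3 and in the tables agree, including whether the nil week is part of it. The doses and the schedule are for the sponsor to set.

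The cost is a wording amendment to sections 3, 6.3 and 6.4 and to the patient instruction sheet. No visits or data items are added, and the statistical analysis is unchanged.

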6.4 DOSE CHANGES

Doses will be initiated as per the example regime in section 6.3. Patients will be allowed to increment the dose more slowly, or to stay at a previously tolerated dose where their symptoms preclude reaching the target dose stated in 6.3. Variation of dose like this will not count as a protocol deviation. Patients will be able to stay on the dose they can tolerate. If necessary, this will be done under close guidance of the researcher. There will be no other changes to the doses described in section 6.3.

6.5 PARTICIPANT COMPLIANCE

Adherence will be monitored by the local hospital sites by phone. Symptoms that might be related to either drug will be assessed using a structured questionnaire given as per the follow-up visit schedule.

As indicated in 7.2 below, during the first month after randomisation, participants will be asked to contact the local hospital investigator if they experience adverse symptoms, or the central team. Once patients are established on their steady dose of tablets, they will be asked to contact the local hospital or the central team if they experience untoward symptoms (in addition to contacting their GP or other relevant hospital service). Such episodes of contact will be recorded in the eCRF or AE form or reported as SAEs as appropriate.

6.6 OVERDOSE

Cilostazol: The SPC for Cilostazol states that there is limited information on the effects of acute overdose in humans. It is anticipated to feature severe headache, diarrhoea, tachycardia and possibly cardiac arrhythmia. Management would be supportive care and gastric lavage as appropriate.

Isosorbide Mononitrate: The SPC describes the expected effects of isosorbide mononitrate in overdose and details measures for management.

The risk of overdose will be mitigated by follow-up phone calls by the hospital research teams at weeks 1-2 and 3-4 and at 6, 12, and 18 months as well as minimised by excluding patients with a history of overdose or suicide.

6.7 OTHER MEDICATIONS

6.7.1 Non-Investigational Medicinal Products

Not applicable.

6.7.2 Permitted Medications

Patients should continue to take prescribed guideline stroke prevention treatment and may continue to take all other usual prescribed medication during the study except those listed in section 6.7.3 and in the exclusion criteria in section 4.3.

Investigators will record the concomitant medications that the participant receives at the time of enrolment or during the trial follow-up in the eCRF.

6.7.3 Prohibited Medications

Isosorbide mononitrate:

Phosphodiesterase 5' inhibitors (tadalafil, sildenafil, vardenafil).

Cilostazol:

Other strong inhibitors of metabolic enzymes CYP3A4 or CYP2C19 (e.g. diltiazem). Erythromycin, clarithromycin, ketoconazole, itraconazole, omeprazole Dual antiplatelet drugs (e.g. aspirin and clopidogrel simultaneously) Anticoagulants (warfarin, heparin, dabigatran, rivaroxaban, apixaban)

Reduction of the dose to 50 mg twice daily is recommended in patients receiving omeprazole, erythromycin, clarithromycin, ketoconazole, and itraconazole.

Although not noted in the BNF, SPCs for cilostazol indicate caution is advised with other strong inhibitors of metabolic enzymes CYP3A4 or CYP2C19, such as simvastatin, atorvastatin, lovastatin, carbamazepine, phenytoin, rifampicin. BNF notes caution with isosorbide mononitrate and hypotensive agents such as diltiazem, hydralazine, etc. No increase in symptoms or SAEs were observed in patients allocated both ISMN and cilostazol in LACI-1 or LACI-2.

Please refer to the SPCs for full details.STUDY ASSESSMENTS

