Since there is little good evidence that guideline stroke prevention improves outcomes in SVD²⁸ or in lacunar stroke^{29,24,26,27} it is very important to confirm the results of LACI-2 in a large phase 3 confirmatory trial. The disparity between the apparent benefits of cilostazol in stroke prevention in the Asia-Pacific region³³ and its lack of use in the UK and other Western countries is striking and supports evaluation.

Treatment under investigation: The ways in which ISMN and/or cilostazol might improve cerebrovascular function by replacing NO which is deficient in SVD and stimulating the PGI2-cAMP system to reduce NO breakdown, amongst other effects, have been outlined

above. Notably, combined stimulation of the NO-cGMP and PGI2-cAMP systems potentially maximises the benefits of each drug, if it does not increase adverse effects. Indeed, the LACI-2 results seem to suggest that cilostazol and ISMN together may be more effective than either drug alone. Although both might also improve BP control, lower BP modestly, and reduce BP variability, we did not see any difference in BP between patients allocated ISMN, cilostazol, both or neither in patients at one year follow-up in LACI-2, nor did we see any increase in falls, dizziness or other symptoms that might be attributable to hypotension. Furthermore, we did not see any excess cranial or systemic bleeding from the combination of ISMN (no antiplatelet effects) and cilostazol (weak antiplatelet), or either drug alone in LACI-2,⁴⁹ when given with guideline clopidogrel or aspirin (both moderate-strong antiplatelet agents),²⁴ providing reassurance about safety. The lack of increase in bleeding with cilostazol including when given in combination with other antiplatelet drugs is consistent with the cilostazol trial data to date.^{33,34}

Both ISMN and cilostazol are off patent, widely available as generics, and inexpensive.

Benefits to participants: About 35000 patients experience lacunar stroke each year in the UK. Currently they receive UK guideline secondary stroke prevention treatment (an antiplatelet drug usually clopidogrel, antihypertensive treatment, a statin and lifestyle advice), but two ESO guidelines (in prep and²⁸) show that these approaches have limited benefit in patients with lacunar ischaemic stroke, reflecting that the mechanism of SVD differs from that of other types of ischaemic stroke.

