4.3 EXCLUSION CRITERIA

General exclusion criteria:

- Less than 24 hours since onset of the lacunar stroke or patient on dual antiplatelet drugs;
- Stroke mechanism with definite treatment indication (e.g. cardioembolism, ipsilateral carotid stenosis);
- Other explanation for the lacunar stroke symptoms (ie recent cortical infarct, haemorrhage or tumour);
- Other active neurological disease (e.g. brain tumour, multiple sclerosis, recurrent seizures, neurodevelopmental disorder well-controlled epilepsy present prior to the lacunar stroke, a single seizure at onset of the stroke, or provoked seizure, is not an exclusion);
- Contraindication to both trial drugs in section 4.3 of the SPCs (patients with a contraindication to one trial drug may still be randomised to the other trial drug);
- Indication for either trial drug (patient already prescribed one trial drug may still be randomised to the other trial drug);
- Dependent (mRS>2);
- Clinical diagnosis of dementia;
- Planned surgery during the trial period including carotid endarterectomy. Note prior and apparently successful carotid endarterectomy (or other surgery) is not an exclusion criterion and patients who would otherwise be eligible but require endarterectomy first may be randomised after recovery from successful endarterectomy;
- Unable to swallow;
- Diagnosis of hypotension, defined as sitting systolic blood pressure less than 100mmHg;
- History of drug overdose or attempted suicide

- Unlikely to be available for follow-up at 18 months;
- Unlikely to comply with study procedures and follow-up procedures for whatever reason (eg history of poor medication compliance) in the opinion of the randomising physician;
- Pregnant, breast-feeding, or of child-bearing potential and not using highly effective contraception as stated in section 10.9 (Pregnancy);
- Renal impairment (creatinine clearance <25 ml/min)
- Hepatic impairment
- Currently prescribed dual antiplatelet treatment (single antiplatelet is not an exclusion); patients can be randomised into the trial once the 28-day period of dual antiplatelet for guideline secondary prevention following the acute lacunar ischaemic stroke has completed;
- Previously enrolled in LACI-3;
- Enrolled in a study that precludes co-enrolment with LACI-3.

Cilostazol exclusion criteria (still allows randomisation to ISMN):

- Definite indication for (i.e. already prescribed) Cilostazol, or definite contraindication to Cilostazol as per SPCs section 6.1.8.

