- Prohibited medications to Cilostazol (see sections 4.5 of the appended SPCs and protocol section 6.7.3).
- Active cardiac disease (atrial fibrillation, myocardial infarction in past 6 months, active angina, symptomatic cardiac failure).
- Bleeding tendency (e.g. known platelets<100, active peptic ulcer, history of intracranial haemorrhage such as subdural haematoma, subarachnoid haemorrhage, intracerebral haemorrhage, but not asymptomatic haemorrhagic transformation of infarction or a few microbleeds, taking anticoagulant medication)

ISMN exclusion criteria (still allows randomisation to Cilostazol):

- Definite indication for (i.e. already prescribed) ISMN, or definite contraindication to ISMN as per SPCs.
- Prohibited medications to ISMN (see sections 4.5 of the appended SPCs and protocol section 6.7.3).

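### Protocol 6.7.3 prohibits five named medicines with cilostazol and also gives a cilostazol dose for patients taking them, a dose change that 6.4 does not allow

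*Protocol*

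**What the plan says.** Four sections of the protocol bear on this point.

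- **6.7.3 (Prohibited Medications)**, under cilostazol, names "Erythromycin, clarithromycin, ketoconazole, itraconazole, omeprazole". It also prohibits strong inhibitors of CYP3A4 or CYP2C19 as a group, as well as dual antiplatelet drugs and anticoagulants. The following paragraph reads: "Reduction of the dose to 50 mg twice daily is recommended in patients receiving omeprazole, erythromycin, clarithromycin, ketoconazole, and itraconazole". A further paragraph, reporting the SPCs, advises caution with "other strong inhibitors of metabolic enzymes CYP3A4 or CYP2C19, such as simvastatin, atorvastatin, lovastatin, carbamazepine, phenytoin, rifampicin".
- **4.3 (Exclusion Criteria)**, under the heading "Cilostazol exclusion criteria (still allows randomisation to ISMN"), has the entry "Prohibited medications to Cilostazol (see sections 4.5 of the appended SPCs and protocol section 6.7.3").
- **6.7.2 (Permitted Medications)** tells patients to stay on guideline stroke prevention and says they "may continue to take all other usual prescribed medication during the study except those listed in section 6.7.3" and in the exclusion criteria.
- **6.4 (Dose Changes)** lets a patient escalate more slowly, or remain at an earlier tolerated dose when symptoms prevent reaching target. It then closes the list: "There will be no other changes to the doses described in section 6.3".

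**The concern.** A patient taking one of the five medicines cannot be both barred from cilostazol and assigned a cilostazol dose. The 6.7.3 list decides who may be randomised to cilostazol versus no cilostazol, so the conflict reaches eligibility as well as prescribing. The same question arises when one of these medicines is started during the 18 months of treatment.

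At stake is consistency across the planned 60 or more sites. One site may exclude such a patient, and another may enrol the patient at the lower dose. A third could enrol on the strength of the dose sentence and then, reading 6.4 strictly, escalate to the full dose. That third path is the one with a safety implication. Statistically, who is in the cilostazol comparison and what exposure they receive would then depend on the site's reading. Randomisation is not minimised by centre (5.5.1). Section 13.2.2 rules out prospective waivers except for an immediate hazard, so a site cannot obtain a case-by-case ruling that departs from the text.

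**Working it through.** The protocol states no figure on this point, so the check sets the sections side by side.

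**Step 1: compare the two lists in 6.7.3.**

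| Medicine | On the cilostazol prohibited list | In the dose-reduction sentence |
|---|---|---|
| Erythromycin | yes | yes |
| Clarithromycin | yes | yes |
| Ketoconazole | yes | yes |
| Itraconazole | yes | yes |
| Omeprazole | yes | yes |

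The overlap is five out of five. The dose sentence covers no medicine that is not also prohibited, so it cannot be read as applying to some other group.

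**Step 2: follow the list into eligibility and conduct.** Section 4.3 excludes from cilostazol anyone on a 6.7.3 drug, while leaving ISMN randomisation open. Section 6.7.2 carves the 6.7.3 drugs out of permitted medication during the study. Both therefore point to exclusion, and the dose sentence is what points the other way.

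**Step 3: follow the dose sentence into dosing.** The cilostazol tables in 6.3 escalate to 100 mg twice daily. A 50 mg twice-daily step appears there only as a stage of escalation and as the end-of-study taper. Under 6.4 a participant could remain at that step because of symptoms, but not because of an interacting drug. A reduction for co-medication therefore falls under the changes that 6.4 rules out.

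**Step 4: look for a rule that reconciles them.**

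- *Timing.* Nothing limits the dose sentence to drugs started after randomisation. Such a limit would still conflict with 6.7.2 and 6.4.
- *Later contraindication.* Section 5.5.1 says a participant allocated both drugs who develops a contraindication to one should discontinue that drug. Section 5.5.3 says to stop in line with the SPC. Neither gives a reduced-dose option.
- *SPCs.* Section 6.7.3 refers to them for full details, and 4.3 cites both SPC section 4.5 and 6.7.3. Neither says which prevails. The SPCs are not at hand and cannot be used to settle the point.

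No reconciling rule is found in the protocol.

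**Step 5: the inhibitor label.** Section 6.7.3 prohibits strong CYP3A4 or CYP2C19 inhibitors as a group, with diltiazem as the example. It then applies the same description to six drugs for which it advises caution: three statins, carbamazepine, phenytoin and rifampicin. One label carries two statuses, although no statin is named on the prohibited list.

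**The case against.** The strongest reply is that the operative rules are clear. Sections 4.3 and 6.7.2 both say exclude, and the baseline eCRF has its own cilostazol eligibility confirmation (7.2). On that view the dose sentence is a stray carry-over from product information. This has force. It narrows the source of the ambiguity to one sentence, and it means that sites may diverge, not that they will. It does not remove the fault: if exclusion is intended the sentence has no function, and if it has a function then 4.3, 6.7.2 and 6.4 are wrong as written.

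It can also be said that either reading taken alone limits exposure to the interaction. That is fair. A safety risk needs the mixed path of enrolling on the dose sentence and then applying 6.4.

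Two stronger inferences are tempting, and the protocol does not support them.

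- **That statin users are barred from cilostazol.** A reader might infer this because 6.7.3 prohibits strong inhibitors and then calls three statins by that name, while section 1.2 describes usual care as "an antiplatelet drug usually clopidogrel, antihypertensive treatment, a statin and lifestyle advice". But 6.7.3 gives those statins the status of caution, 6.7.2 tells patients to continue guideline prevention, and the Trial Summary names lipid lowering as part of it. What remains is a duplicated label.
- **That the cilostazol comparison loses a calculable amount of power.** Take the 9.1 control distribution, OR 0.70, two-sided 5% and 15% losses. The evaluable number is N = 1300 × (1 − f) × 0.85, where f is the share excluded from cilostazol. Whitehead's formula gives V = (N/12)(1 − Σp̄³), with Σp̄³ = 0.0813, and power = Φ(|ln 0.70|√V − 1.96). For f = 0, 10, 20 and 30% the power is 90.7, 87.5, 83.5 and 78.4%. The arithmetic holds, but the fractions are assumptions with no source in the protocol. Section 9.1 sizes the trial on ISMN and supports OR 0.70 with ISMN and combination results. Other cilostazol exclusions already make 1300 an unrealistic starting point. The figures do not measure this defect.

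**Conclusion.** The contradiction stands and is complete for the five named medicines: 6.7.3 prohibits them with cilostazol and gives a cilostazol dose for patients taking them. Sections 4.3 and 6.7.2 enforce the prohibition, and 6.4 does not allow the dose change. As a result sites may differ on entry to the cilostazol comparison, on continuation in it, and on dose. The size cannot be estimated, since the protocol gives no frequency of use. The conclusion rests on the protocol text alone and assumes nothing about what the SPCs say. ISMN randomisation of these patients is unaffected. The double use of the inhibitor label is a lesser wording fault and does not amount to an exclusion of statin users. Because the conflict concerns eligibility and dosing of an investigational drug and is cheap to resolve, it should be corrected.

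**What to change.** The sponsor should reconcile 4.3, 6.4, 6.7.2 and 6.7.3 so that each named medicine has exactly one status (prohibited, subject to a dose instruction, or caution) and carries it through all four sections. The status should be stated separately for a medicine already taken at entry and for one started after randomisation. If any dose instruction is kept, 6.4 has to provide for it; if none is kept, the sentence in 6.7.3 has to go. The section should also stop using one inhibitor label for two statuses. Which status or dose applies to each medicine is for the sponsor's clinical and pharmacy leads, and no view is taken here.

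The cost is a protocol amendment to a few short paragraphs, with matching guidance to site pharmacies. No new data collection is needed, because 6.7.2 and 7.2 already require concomitant medication to be recorded.
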